Objective 1: To evaluate the comparative effectiveness of patient-centered messages to enhance clinical trial participation, through a culturally tailored website, accessed using iPads, versus NYU's standard clinical trial participation website.

Hypothesis 1: Participants exposed to tailored messages about clinical trial literacy will exhibit greater likelihood in participating in clinical trials than those exposed to NYU's standard website.

Objective 2: To determine whether psychosocial factors (awareness of clinical trial, intrinsic motivation, health literacy, and self-efficacy) and medical factors (risk behavior, history of preventive behavior, and clinical diagnoses) mediate greater likelihood of participating in clinical trials among individuals exposed to the intervention.

[figure not shown]
Hypothesis 2: Greater likelihood of participating in clinical trials will be mediated by greater health literacy and self-efficacy independent of other individual-level factors (medical, knowledge, attitude/beliefs, and intrinsic motivation) and contextual-level factors (social support and socio-economic position).

Study Design

Objective 1: To evaluate the comparative effectiveness of a culturally and linguistically tailored clinical trial literacy website in increasing likelihood of participating in clinical trials. To achieve this objective, we will use a randomized group design, assessing the following patient-centered outcomes: willingness to enroll in clinical trials and behavioral intent as well as likelihood of referring others to enroll in such trials) before and after exposure to a culturally-tailored clinical trial literacy website. Health literacy will be measured both before and post exposure to tailored messages.

Participants will be randomized into two groups. The intervention group (n=50) will have access to culturally tailored website. Participants in the control group (n=50) will have access to NYU 's standard trial participation website.

Study Flowchart

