Participants randomized to the control condition will have free access to the NYU standard clinical trials website. Currently, there is no specific comparative effectiveness data evidencing superiority of any website or other format for increasing clinical trials literacy. Furthermore, there has been previous research to suggest the overall difficulty that patients have in using generic, versus tailored clinical trial materials. This, our study will ascertain effectiveness of a tailored website compared to the standard website. Participants in the control condition will have access to the tailored website at the date of study completion (no later than 6 months' post-date of enrollment).

2. Process of Consent

We will explain to participants that the purpose of the study is to understand barriers pertaining to why blacks do not participate in clinical trials, assess their willingness to enroll in clinical trials, and ascertain whether or not they will refer others to participate in such trials. We will obtain participants consent to audio-record the debriefing session. The screening team will comprise ethnically concordant investigator: [name]. All participants will be reminded that their responses are confidential and that they may refuse to participate in the project or withdraw at any time without explanation, and further, that such action will in no way affect their future interactions with their health care provider, or with New York University Medical Center. To ensure confidentiality, data will be associated with an individual participant only by an assigned identification number, the code for which will be kept in a locked drawer that only the study investigators will have access to.

3. Number of subjects.

The proposed study expects to recruit a total of 100 participants from all recruitment strategies over a period of 9 months.

4. Gender of Subjects.

The study will include black men and women

5. Age of Subjects.

The sample frame will include black men and women 18 years old and older.

6. Racial and Ethnic Origin.

Our emphasis on blacks is justified by the low participation in clinical trials in this group.

7. Inclusion Criteria.

Self-reported race/ethnicity as African American, African, Caribbean American or black men and women; ages ≥ 18 years; accessible by telephone; no plans to move away from the region within the year following enrollment; consent to participate.

8. Exclusion Criteria.

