Analysis: We will examine the path toward greater participation in clinical trials using Structural Equation Modeling (SEM). SEM will determine influences of mediating/moderating factors on the role of tailored messages in improving participation rates in existing clinical trials. Specifically, we will use moderated path analysis from Baron and Kenny's model. We chose these factors based on research showing acceptable effect size in predicting likelihood of increased participation. Alternatively, we will employ probabilistic modeling methods (e.g., Bayesian Belief Network) to investigate interactions (omni-directionality) among predictors and different pathways to the desired study outcomes, determining which factors best differentiate cases and controls. Thus, we will ascertain patient characteristics most likely to show improvement in rates of participation.

V. STATISTICAL PLAN

Power Calculations: Primary Objective: Assuming a medium effect size ($d = 0.32$), as derived from Cohen, and a sample size of 100, the study will be adequately powered (> 80%) to detect significant differences between participants likely to show improvement in health literacy scores and those who are not using Fisher's Exact tests (critical $X^2 = 6.58$). This will also permit detection of a significant increase in the number of participants in the intervention arm opting to register for clinical trials. In a previous pilot study, we found that 45% of minority patients in the community adopted recommendations for medical treatments after exposure to tailored health messages, which compares to 25% who did without such exposure. Assuming a 20% increase in the likelihood of adopting health messages and a sample size of 100, the proposed study will have adequate power for a preliminary test of the hypothesis that exposure to health messages will foster greater uptake of tailored health messages and improvement in clinical trial health literacy level. Achieving the goal of a 20% increase would have an important public health impact regarding adoption of messages about clinical trials. A two-tailed test, with 80% power and $\alpha = 0.05$ comparing 25% to 45% requires 50 participants per arm. The study is powered to assess differences in participation rates between the two arms as well as the mediating effect of individual and contextual factors between tailored clinical trial messages and participation rates, considering a 23% attrition rate.

VI. DATA HANDLING

Confidentiality

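### Section V claims power for the mediating effect without any calculation, and the calculations it does show cannot support that claim

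*Combined protocol and SAP*

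**What the plan says.** The last sentence of Section V claims power for the difference in participation rates between arms "as well as the mediating effect of individual and contextual factors between tailored clinical trial messages and participation rates", "considering a 23% attrition rate". Section II, item 3 sets the size: "The proposed study expects to recruit a total of 100 participants", split 50 and 50 (Study Design, Objective 1).

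Section V shows two calculations. One takes an effect size of 0.32 with N=100 and a Fisher/chi-square test, and claims more than 80% power for improvement in health literacy. The other is a two-sided test at alpha 0.05 with 80% power: "comparing 25% to 45% requires 50 participants per arm". Its rates come from an earlier pilot on adoption of treatment recommendations.

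The mediation analysis is in Section IV under Hypothesis 2. It is a structural equation model, specified as moderated path analysis from Baron and Kenny's model, with a Bayesian belief network as the alternative. Objective 2 lists seven candidate mediators. Hypothesis 2 singles out health literacy and self-efficacy, independent of further individual and contextual factors. The only reference to effect sizes for these factors is that earlier research found them acceptable; no number is given.

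**The concern.** A power statement needs an effect, a test and a sample size. For mediation, Section V supplies only the sample size. An indirect effect is the product of two paths (website to mediator, and mediator to participation given arm), and neither path is given a value. It is also unclear which effect is said to be powered, because Section V refers to individual and contextual factors in general, whereas Hypothesis 2 names two mediators.

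At stake is how Objective 2 is read. If the analysis is reported as adequately powered, a non-significant indirect effect invites the conclusion that the factor is not a mediator, when the study may simply have been too small to show it. The plan sets no rule for interpreting null mediators, so nothing in it guards against that reading.

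**Working it through.** **Inputs from the documents.** N=100, 50 per arm; attrition 23%, so 100 × 0.77 = 77 completers (38.5 per arm); two-sided alpha 0.05; rates 25% and 45%; effect size 0.32. No mediation path is given, so all path sizes in steps 3 to 5 are assumptions.

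**1. The plan's two calculations.**

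*25% versus 45%.* n per arm = [1.96·√(2·0.35·0.65) + 0.842·√(0.25·0.75 + 0.45·0.55)]² / 0.20² = (1.322 + 0.555)² / 0.04 = 88.1, so 89 per arm. The stated 50 is not reproduced. One-sided (70), continuity-corrected (98), unpooled (86) and arcsine (88) versions do not give 50 either.

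*Effect size 0.32.* Read as Cohen's w with 1 degree of freedom, N = (1.96 + 0.842)² / 0.32² = 76.6, and 76.6 / 0.77 = 99.5. Power is 89% at N=100 and 80.2% at N=77. On this reading both the claim of more than 80% and the 23% attrition reproduce, but for a single 2×2 test and not for an indirect effect.

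**2. Ceiling if Baron and Kenny's total-effect step is required.** Every step must then be significant, so power cannot exceed that of the total-effect test. That power is Φ[(0.20·√n − 1.322) / 0.6595]:
- n=50: (1.414 − 1.322) / 0.6595 = 0.14, power 55.6%.
- n=38.5: (1.241 − 1.322) / 0.6595 = −0.12, power 45.1%.

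Fisher's exact test gives 47.7% and 40.9%. A larger mediator effect does not raise the ceiling.

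**3. Without that step: the first path alone.** For a two-sample t-test the noncentrality is d·√(N/4). Power of 80% needs d=0.57 at N=100 (0.566 × 5 = 2.83) and d=0.65 at N=77 (0.647 × 4.387 = 2.84). Since both paths must be significant, this is a floor even when the second path is certain to be detected.

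**4. Both paths.** Assumptions: one mediator, continuous outcome, no baseline adjustment, no covariates or moderators. First-path power is from the noncentral t. Second-path power uses Fisher's z for a correlation r given arm, Φ[atanh(r)·√(N−4) − 1.96]:
- r=0.4: 98.6% at N=100, 95.2% at N=77.
- r=0.2: 51.0% at N=100, 41.0% at N=77.

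The product approximates the power to find both paths significant. The last column is the simulated value.

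| Arm effect on mediator | Mediator-outcome path | N=100 | N=77 | Simulated, N=100 / N=77 |
|---|---|---|---|---|
| 0.5 SD | 0.4 | 0.697 × 0.986 = 0.69 | 0.581 × 0.952 = 0.55 | 69% / 55% |
| 0.68 SD | 0.4 | 0.920 × 0.986 = 0.91 | 0.838 × 0.952 = 0.80 | 90% / 80% |
| 0.8 SD | 0.2 | 0.977 × 0.510 = 0.50 | 0.934 × 0.410 = 0.38 | 49% / 38% |

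**5. Binary outcome.** With participation fixed at 25% versus 45% and a mediator odds ratio between 1.5 and 6 per SD, simulated power at 77 completers is 19–60% for 0.5 SD on the mediator and 31–93% for 0.8 SD. The second path again matters as much as the first.

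**The case against.** The best defence has four parts.

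- **A large website effect is not needed.** A reader might infer from the small sample that mediation is detectable only if the website's effect on the mediator is large. The figures do not support that. With a mediator-outcome path of 0.4, power passes 80% at about 0.6 SD for N=100 (83%) and at 0.68 SD for N=77, between the conventional medium (0.5) and large (0.8). Nor is a large effect sufficient, as the last table row shows. The plan's 0.32, read as w, corresponds to d = 2·0.32/√(1 − 0.32²) = 0.68, which clears the first path. This part stands. It changes how the size should be described, but it does not supply the missing calculation.
- **Baseline adjustment could help.** Table 1 schedules Internet self-efficacy and clinical trials literacy at baseline, 1 month and 3 months. With an assumed baseline correlation of 0.5 to 0.7, the first-path requirement at N=77 falls to 0.647·√(1 − ρ²), that is 0.56 to 0.46 SD (0.49 to 0.40 at N=100). At a correlation of 0.7, 0.5 SD with a path of 0.4 would give 0.858 × 0.952 = 82% at N=77. The design permits this, but the mediation plan does not state it, and it does not lift the total-effect ceiling.
- **The total-effect step may not be intended.** The plan cites the Baron and Kenny model without saying that every step must be passed. The ceiling is therefore conditional.
- **It is a pilot.** The background calls it one, and Section V speaks of a preliminary test. That lowers the stakes, but it does not qualify the sentence claiming power for mediation.

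**Conclusion.** The mediation power claim is wrong as written: the sentence asserts a property that nothing in the documents establishes. Under the model the plan names, with the total-effect step required, the property is not delivered at the plan's own rates: power is at most about 56% with all 100 participants and about 45% with 77 completers.

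Without that step the answer depends on two paths that the documents do not give. At 77 completers, 80% needs at least about 0.65 SD on the mediator (less with baseline adjustment) together with a strong mediator-outcome association. These figures assume one mediator and a continuous outcome; the covariates and moderation terms in the plan were not modelled.

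Two stronger conclusions are not supported. It does not follow that the study cannot detect mediation, since some plausible path sizes reach 80%. It also does not follow that Objective 2 must be cut to the two mediators in Hypothesis 2; that would narrow a stated objective and is a matter of preference.

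**What to change.** In the last sentence of Section V, delete "as well as the mediating effect of individual and contextual factors between tailored clinical trial messages and participation rates", so that no power is claimed for mediation.

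In Section IV under Hypothesis 2, and with Objective 2, add wording such as: *The mediation analyses are exploratory and the study is not powered for them. Indirect effects will be reported as estimates with confidence intervals. A non-significant indirect effect will not be interpreted as evidence that a factor is not a mediator.*

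If the sponsor prefers to keep a power claim, it should name the mediator, the outcome and the two assumed path sizes. It should also say whether the total-effect step is required and whether the mediator is adjusted for baseline, and give a simulated power at 77 completers.

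The cost of the recommended change is a weaker claim for a secondary objective. Sample size, visits and data collection are unaffected.
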